## Risk/Benefit Assessment

Protection against Risk:

- 1) **Disclosure of protected health information.** All human subjects' data will be stored in a restricted access folder behind the VA firewall on a server meeting Federal Research Data Security requirements. Only study staff listed on the IRB staff listing will have access to the folder, and all computer access requires a PIV card and password. Data will not be transferred outside of this environment.
- 2) **Nominal Group Technique.** An experienced qualitative researcher will conduct the nominal group sessions with PACT providers. Participation in the sessions is voluntary, and steps will be taken to reduce social desirability and psychological discomfort during the session including using anonymous responses on index cards and anonymous ranking sheets.

Potential Benefits of the Proposed Research to Human Subjects and Others:

- 1) **Benefits to PACT providers.** All PACT providers will be provided with educational materials to improve their knowledge of osteoporosis screening guidelines..
- 2) **Benefits to Veterans.** If the new screening models are effective, Veterans will benefit from improved fracture prevention services, with fewer expected to suffer painful and debilitating low-trauma fractures.

## Selection of Subjects

PACT Providers (n=78, estimated 48 at DVAHS and 30 at RVAMC) include the medical provider (MD or advanced practice provider, APP) and registered nurse (RN) who provide primary care to a panel of 60 or more eligible male Veterans for osteoporosis screening. If the PACT does not have an RN assigned to the team, the PACT provider may participate alone. Providers will be identified by the ACOS and ACNS for Ambulatory Care at each site. Eligible PACT medical and RN providers must be:

- Completed training (i.e., PACT teams led by residents and fellows are excluded, unless supervised by faculty physicians)

- Care for male Veterans  $\geq 65$  years (i.e., Women's Health PACTs are excluded)

Patients (estimated n at both sites = 2376; 1462 at DVAHS) include men aged 65-85 years eligible for primary osteoporosis screening within enrolled PACT teams. Patients will be identified using Corporate Data Warehouse queries. Inclusion criteria:

- No prior fracture or osteoporosis diagnosis
- At least 1 VA Undersecretary Guideline risk factor (weight loss  $>20\%$  in 5 years; BMI  $<25$  kg/m $^2$ ; diabetes; pernicious anemia; gastrectomy; anticonvulsants; glucocorticoids; androgen deprivation therapy; hyperthyroidism; hyperparathyroidism; rheumatoid arthritis; alcohol dependence; chronic lung disease; chronic liver disease; stroke; Parkinsonism; prostate cancer; and current smoking).

Exclusion criteria:

- Active non-skin cancer diagnosis
- Enrollment in hospice or palliative care

Patients (year 4/5 sub-sample) (estimated n at both sites =900) include men aged 65-85 years, enrolled in eligible PACT team for at least 2 years, who met 1 or more criteria for osteoporosis screening as the protocol at PACT enrollment.

Exclusion criteria:

- Dual Energy X-ray Absorptiometry measurement  $<18$  months prior to outcome measurement period (minimum time required to detect a difference in BMD)
- Active non-skin cancer diagnosis
- Receiving hospice or palliative care
- Lacks capacity to provide informed consent (missing two items on the Evaluation to Consent Measure)
- Inability to transfer independently to DXA table (over scanner weight limit, spinal cord injury, bilateral lower extremity amputation)

## Subject Recruitment

The intervention is focused on the PACT medical and RN providers; therefore, both will be asked to provide verbal informed consent for participation in all training and data collection activities. Study procedures will be described to PACT providers during a monthly Ambulatory Care meeting, with written study informational materials distributed via VA Outlook email. During the meeting participant may be given low-valued promotional items. Study personnel will follow-up individually with each provider to answer questions and complete the informed consent process. Both the PACT provider and RN must agree to participate. As PACT providers turnover in our health system, patient panels are left intact and a new provider assigned; study team members will therefore approach the new provider to request continued participation in the group randomized.

In year 3, a sub-sample of medical providers and RNs whose PACTs have participated in the care models will be recruited for a 1-hour Nominal Group session to collect qualitative data about their experience with the care model. Study staff will send out an informational Outlook email to the work address of all participating PACT providers. Those expressing interest will be contacted individually to provide more information and schedule their participation in the session. Written informed consent will be complete at the beginning of the session, as described below.

In year 4, an additional sub-sample of patients will be recruited to complete a DXA scan. Subjects will be contacted for participation in this outcome measurement regardless of whether or not they were screened during the study period; however, those screened  $<18$  months prior to the outcome assessment will be excluded since the minimum recommended time between DXA scans is 18 months. Study staff will schedule DXA at their closest VA facility. Subjects will be provided \$50 compensation for their time and travel. All subjects and their PACT providers will be provided with their DXA results for clinical decision making.

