## Design

Pragmatic group randomized trial of PACT teams (n=39 teams recruited, estimated 24 at DVAHS and 15 at Richmond VAMC) will be randomized into 2 groups: a control group (no additional support, and a centralized Bone Health Service (BHS) model. Outcomes for all patients eligible for osteoporosis screening within the randomized PACTs will be assessed by investigators masked to group assignment via EHR at baseline and 2 years. Outcomes for PACT providers will be assessed using qualitative methods (nominal group technique).

**Outcome measures** are listed in the table 1 below.

Table 1. Outcome measures by Aim. RDW=Regional Data Warehouse; MPR=Medication Possession Ratio; FRAX=Fracture Risk Assessment Tool.

Outcome	Definition/Measure	Data Source/Timing	Important Difference
Patient (Panel) Level (Aim 1)			
Screening Rates	Proportion of eligible men screened in last 12 months	RDW at baseline, year 1 and year 2	25% increase from 6% Control
Medication Initiation	Proportion of screened men meeting treatment threshold (T score $\leq -2.5$ or FRAX score high-risk) who receive at least 1 prescription	RDW, intervention period year 1 and year 2, non-VA medication lists by chart abstraction.	30% increase from 55% Control
Medication Implementation	Days of medication dispensed divided by follow-up days	Pharmacy dispensing records, for patients started within prior year at baseline, year 1 and 2. Non-VA medication lists by chart abstraction.	20% increase in MPR $>80\%^{14}$ from 30% Control
Medication Discontinuation	Time between first prescription dispensing date and the date of first medication possession gap of $\geq 3$ months	Pharmacy dispensing records, for patients started within prior year at baseline, year 1 and 2. Non-VA medication lists by chart abstraction.	20% difference
Bone Mineral Density	BMD g/cm  at femoral neck and lumbar spine in random sample of men eligible for screening	Random sample of 712 men (356 UC, 178 each of the other 2 models) eligible for screening in panel at least 1 year, measured 2 years after start date	Post-intervention between group difference of 3% femoral neck, 5% lumbar spine 
Harms	Proportion of men started on oral medication for new GI distress in 3 months  Subtrochanteric fractures or Osteonecrosis of the jaw	RDW ICD10 codes, new prescription for proton pump inhibitor or H2 blocker.  RDW ICD10 codes	15% increase from 30% Control  >expected 1/50,000 patient years treatment

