propensity score matching) to make the groups conditionally equal. The parameter of interest will be the Group mean (and standard error) over time, and measured by the ‘average’ PACT value at each time point. Finally, we note that the estimation models above can be adapted to

outcomes distributed other than normal, including Poisson (for number of events/time) and binary (for binary events). This is a 2 group by 3

[figure not shown]

Figure 6. Markov model for Aim 3 analyses of economic impact of 3 screening models.

yearly time point design. To control the overall Type-I error level, we will use the baseline time point as a baseline covariate, and assess group differences at the following time points controlling for baseline. Level of statistical significance will be set at 0.05 (two-tailed) for all tests. In this work, we proposed a GroupxTime interaction, using the time effects as classes/factors. Depending on the significance of this omnibus test, we can assess tests of individual differences (say, group differences at a specific point) by gate-keeping strategy. In the case where the omnibus group by time interaction is significant, then, these will be done without a Type-I error penalty. Initially, we will assess a Time by Group interaction (on 1 degree of freedom). If that effect is declared statistically significant, we will perform follow-up tests to determine where the group differences exist at each follow-up time point, using the gate-keeping strategy listed above. If the Group by Time interaction is not significant, then the main effects of Group and Time will be tested.

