Screening Tool calculation. We do not expect attrition as new patients are added as others leave with relatively constant panel size. Finally, we determine power for the single degree of freedom contrast of import – Usual Care vs. BHS groups across the follow-up time points. For each of the individual outcomes, assumptions and power requirements are listed in the Table. A sample size of 39 PACTs (19 BHS vs. 20 Usual Care) with an average 100 patients / PACT provides over 85% power for all our primary patient-level outcomes, except fracture rates - an exploratory analysis.

Table 6. Power calculation assumptions for Aim 1

Outcome	Assumptions, Minimal Clinically Significant Difference	Power for 39 PACTs and 3900 patients
Screening Rates (PACT level)	6% Usual Care, 40% new models	>0.99
Osteoporosis Treatment	Assume 25% of screened meet treatment thresholds. 30% increase from 55% Usual Care	>0.99
Medication Adherence	Usual Care MPR 0.60 (SD 0.35). 20% increase	0.85
Bone Mineral Density (BMD) Femoral Neck in random sample of high-risk patients	0.939 g/cm  in BHS group vs. 0.967 Usual Care with SD pooled =0.133	0.90 for random sample of 952 patients (25/team); 0.80 for 712 (19/team)

**Missing data Strategies.** As is standard in administrative databases, the absence of a diagnosis code (e.g., fracture) will be assumed to indicate that the event did not occur, and coded by default as 'not present'. For continuous measures where zero is illogical, we will impute a value, simulate and use bootstrapping to derive estimates of effect with appropriate standard errors. To implement the multiple imputation techniques for primary analyses, we will use preliminary analyses of such associations, including graphical displays, to investigate the plausibility of the assumptions underlying the imputation model employed. Further, we will use 25 or more imputed data sets, with FU bootstrapped estimates in order to reduce the impact of the random sampling.

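### Outcome BMD is scanned at each Veteran's closest VA facility, but the analysis has no scanner or facility term, which can cost precision on the power-limiting endpoint

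*Protocol*

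**What the plan says.** **Outcome.** Protocol Table 1 (Design) defines BMD in g/cm² at "femoral neck and lumbar spine in random sample of men eligible for screening", "measured 2 years after start date". The important difference is stated as "Post-intervention between group difference of 3% femoral neck, 5% lumbar spine".

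**Where the scan is done.** Under Subject Recruitment, "Study staff will schedule DXA at their closest VA facility"; the Consent Process section says the same. Men are approached whether or not they had a DXA during the study, so a baseline study scan does not exist for all of them. The payments section calls the scan a repeat, but selection does not require an earlier one.

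**Model.** The Protocol (Aims 1 and 2) and the SAP's Revised Analysis Plan give the same model: PACT and individual as random effects, group and time as fixed effects, with room for covariates. Neither document names a scanner or facility term for BMD. Neither mentions cross-calibration, phantom checks, a common scanner model or central reading. Practice site is collected in three categories (rural CBOC, urban CBOC, VAMC) and is not named for the BMD model.

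**Randomisation.** PACTs were stratified by provider type and blocked by specific site, with small CBOCs combined where numbers were short. The dropped arm was re-randomised to the two remaining arms, and no stratification or blocking is stated for that step.

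**Power.** BMD is called the power-limiting endpoint. Table 6 assumes "0.939 g/cm 2 in BHS group vs. 0.967 Usual Care with SD pooled =0.133" and gives power "0.90 for random sample of 952 patients (25/team); 0.80 for 712 (19/team".

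**The concern.** Two densitometers can read the same hip differently. When the outcome is a change within one man on one machine, a constant offset cancels. Here the outcome is a single absolute value, and the planned baseline covariate cannot remove the instrument's level because no study baseline DXA exists for everyone. Any offset between facilities therefore stays in the data.

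The target is small: 0.967 − 0.939 = 0.028 g/cm². If men on the same team tend to use the same scanner, offsets appear as differences between teams. The model then attributes them to the PACT random effect, and the standard error of the arm contrast grows. The trial would lose power on the endpoint that set its sample size, although a recorded variable could remove that variation.

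**Working it through.** **1. The plan's own figure.** Inputs from Table 6 are a difference of 0.028, SD 0.133 and about 1:1 allocation. The test is two-sided: "Level of statistical significance will be set at 0.05 (two-tailed) for all tests". The two-sample formula with 476 and 356 men per arm gives 0.901 and 0.802, so the stated 0.90 and 0.80 reproduce. They do so only with no design effect for PACT. The power figures below start from that same optimistic base and are meant for comparison with each other.

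**2. Precision when scanner follows health system (assumed).** Take the estimated 24 Durham and 15 Richmond teams, with 12 + 7 in BHS and 12 + 8 in Usual Care (balanced blocking), 25 men per team and one scanner per health system. Let o be the offset. The documents give no offset; 0.0475 is 5% of a BMD of 0.95.

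- Sampling variance of a team mean: 0.133²/25 = 0.000708.
- Variance added to the residual when scanner is ignored: (24 × 15/39) × o²/37, which is 0.000100 at o = 0.02 and 0.000563 at o = 0.0475.
- Model SE = √[(0.000708 + added) × (1/19 + 1/20)] = 0.0085, 0.0091 and 0.0114 at o = 0, 0.02 and 0.0475.
- The true spread of the estimate stays near 0.0085, because blocking balances the scanners. The reported SE is therefore too large.
- Residual imbalance: 12/19 − 12/20 = 0.032, which shifts the estimate by ±0.032 × o.
- Power ≈ Φ[(0.028 ± 0.032 × o − 2.026 × SE)/0.0085], where 2.026 is the t quantile on 37 df.

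| Offset (g/cm²) | Power, no scanner term, less favourable sign | Other sign | Power with scanner term |
|---|---|---|---|
| 0 | 0.90 | 0.90 | 0.89–0.90 |
| 0.02 | 0.85 | 0.88 | 0.89–0.90 |
| 0.0475 | 0.65–0.66 | 0.77 | 0.89–0.90 |

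Simulation of team means agrees to within about 0.01.

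**3. More scanners (assumed).** Simulations used 39 teams, 25 men per team, allocation blocked by site, and 2, 6 or 10 scanners with all of a team's men on one scanner:

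| Between-scanner SD (g/cm²) | Power without term | Power with term |
|---|---|---|
| 0.01 | 0.86–0.88 | 0.88–0.89 |
| 0.02 | 0.78–0.83 | 0.88–0.90 |
| 0.03 | 0.62–0.75 | 0.89 |

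Type I error without the term was 0.007 to 0.047, which is conservative.

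**4. Chance imbalance from the re-randomisation.** Assume 13 teams (39/3) in the dropped arm, re-split 6:7 without blocking, the other 26 teams balanced, and one scanner per team. If a share p of teams uses scanner A, the number among the six sent to one arm has variance 6 × 7/12 × p(1 − p) = 3.5 p(1 − p). The SD of the arm difference in scanner share is √[3.5 p(1 − p)] × (1/19 + 1/20), which is 0.088 at p = 0.3 and 0.096 at p = 0.5. An imbalance of 0.10 shifts the contrast by 0.002 g/cm² at an offset of 0.02 (7% of 0.028) and by 0.0048 at 0.0475 (17%). The contrast's SE under the plan's inputs is 0.133 × √(2/476) = 0.0086.

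**The case against.** **Bias.** A reader might infer that the missing term produces a spurious arm difference. The documents do not support that. PACTs were blocked by specific site, so both arms draw on the same catchments and their scanner mix should be alike in expectation. What imbalance remains is due to chance. Simulated type I error was at or below 0.05 under blocking and 0.049 to 0.062 without any blocking. This objection stands.

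**Size of imbalance.** Treating all 39 teams as allocated without blocking gives an SD in scanner share of about 0.15 to 0.16. That ignores the stated blocking. The textual routes to imbalance are the combined small CBOCs and the re-randomised arm, and the latter gives 0.09 to 0.10 under the assumptions above.

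**Adjusting for practice site.** It is tempting to say that site adjustment could not help because the scan location follows the man's address. If teams share a scanner, site adjustment would capture much of the difference, although the three recorded categories are coarser than facility.

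**Scanner use within teams.** If scanner varied from man to man independently of team, the share imbalance would have SD √(0.25 × 2/476) = 0.032. The power cost would then be slight: 0.892 against 0.90 at an offset of 0.05. The larger losses need scanner use to cluster by team.

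**Unknown inputs.** The number of facilities, the makes and any offset are absent from the documents, so the loss could be trivial. The model also allows covariates, so facility could be added later. That is true, but a term chosen after seeing the data is weaker than one specified beforehand.

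**Conclusion.** The point holds as an omission that may cost precision, and not as a demonstrated bias. An absolute BMD value from the nearest facility is analysed with no scanner or facility term and no described cross-calibration, against a target of 0.028 g/cm². The cost depends on scanner differences that the documents do not give and on whether teams share scanners. It ranges from nothing with like, cross-calibrated machines to a fall from about 0.90 to 0.66 with two scanners 0.0475 g/cm² apart. The chance imbalance left by a re-randomisation without blocking is secondary. The term recovers nearly all the lost power when offsets exist and costs almost nothing when they do not, so it should be specified.

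**What to change.** - Record facility and scanner make and model with each outcome DXA.
- Before unblinded analysis, specify scanner (or facility, with sparse ones pooled) as a fixed effect in the femoral neck and lumbar spine BMD models.
- Where manufacturers differ, analyse standardised BMD.
- Report scanner mix by arm, and state whether the re-randomisation kept the site blocking.

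The cost is one data field, a short addition to the SAP and a few degrees of freedom. Where teams share one scanner, some of these come from the cluster level, where about 37 are available (39 teams less two group means). In the simulation with 10 scanners, power with the term was still 0.88 to 0.89.

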## Consent Process

[figure not shown]
If a PACT provider expresses interest in participation, a study staff member will arrange a time for them to meet to further describe study procedures, risks, and benefits. When possible, this meeting will occur in-person in the PACT staff workroom or other quiet workplace location; however, providers in Community Based Outpatient Clinics may choose to have VA Skype for Business or telephone meetings to accommodate their schedules. Study staff will distribute copies of the Participant Consent Handout to each provider prior to the meeting so they are available for review during the meeting.

Once the informational meeting has been completed and PACT team members have had a chance to ask any questions, the study staff will encourage them to discuss privately whether or not they wish to participate. This may occur immediately after the meeting, or they may choose to take several days to consider. If providers choose to participate, they will be asked to provide verbal informed consent to 2 study staff members; a waiver of documentation of informed consent is requested for this process. As a way to thank subject and to promote the project, participants will be given promotional items such pens, badge holders and Bluetooth speakers with study logos.

In year 3, a subset of PACT medical providers and RNs will be recruited for the Nominal Group sessions as above. Each will be sent an electronic copy of the informed consent document via VA Outlook email prior to the session to review individually. As each staff member arrives, a study staff member will review the procedures, risks, and benefits with each individual or small group. They will have the opportunity to ask any questions and will be informed that they can leave now or at any time during the session. If they wish to participate, they will be asked to sign 2 copies of the informed consent, HIPAA authorization, and notice of privacy practices, keeping 1 set for themselves and giving the other set to the study staff.

In year 4, a subset of Veterans receiving a DXA scan will be contacted, screened and consented, which, study staff will schedule a scan at closest VA facility to the Veteran. For completing the DXA scan, participants will be compensated \$50 for their time according to VA compensation policies.

A waiver of patient informed consent and HIPAA authorization is requested for patient outcomes assessment via the EMR because is a low risk study implementing routine clinical care as currently recommended by the VA Undersecretary.

PROSPR model step and screening model.

## Study Interventions

**Randomization.** At the beginning of the project stratified, block randomization was used to randomize all providers. Randomization will occur at the level of PACT team. PACT teams

were stratified by medical provider type and blocked by site (e.g., specific CBOC/VAMC). A statistician unaware of team identity randomized PACTs in blocks of 3 within strata to ensure similar distributions. If insufficient numbers of PACTs were recruited within small CBOCs, they were combined with other similar CBOCs (rural vs. urban) for randomization. In light of the VA's response to COVID-19 efforts and demand on PACT providers, PACT teams participating in the PACT practice management arm will be re-randomized to either the Bone Health Service or Control arms to decrease burden and continue participation in the project.

For the sub-sample of participants recruited starting in year 4, Veterans will be randomized using a random number generator. Each eligible Veteran will be contacted in order until the target number in each PACT have provided informed consent for BMD measurement (total n=900).

**Interventions.** Initially two screening models will be compared to control. Each includes 2 main categories; 1) osteoporosis screening promotion, and 2) medication adherence promotion. Figure 6 depicts the main intervention components and outcome measures as they relate to the PROSPR conceptual model.

**Note that Veterans in all enrolled PACTs receive guideline-recommended “usual clinical care” for osteoporosis screening delivered by a VA clinical provider and endorsed by their primary care provider. In this situation, the “intervention” is how the model organizes responsibility and support for this care.** Table 2 describes how the steps differ between the screening models and which providers are responsible for them.

**Control**— PACT providers in the control group will be given the VA Undersecretary Guidelines for primary osteoporosis screening and standard patient education materials for adherence support without additional support. This arm represents a “no practice management support” control group.

**PACT Practice Management Model.** This model represents a robust practice management support model, with multiple tools and processes to facilitate osteoporosis care. In addition, it adds an adherence support component. All components are implemented by PACT providers, who will receive 1 hour of individualized instruction by study staff in their clinics at the beginning of the study period. The VA's COVID-19 response has increased demand on PACT providers. With input from stakeholders including PI's, statisticians and providers and the ACOS, to decrease the time burden on PACT providers assigned to this arm, the study team will re-randomize and re-consent PACT team, therefore, eliminating PACT practice management activities and analysis.

**Bone Health Service Model** – Patients in PACTs randomized to the BHS model will have osteoporosis screening, education, and follow-up handled centrally by the bone health team. PACT providers can opt out of the service for patients in whom they believe it is not appropriate, and approve all orders, but are not responsible for most activities.

